7.3.5 Amendment 1, 18 May 2020

Main Rationale for the Amendment:

The main purpose of this amendment was to incorporate the following modifications requested by the FDA Center for Biologics Evaluation and Research:

- Enhance monitoring of participants who are confirmed to have SARS-CoV-2 infection.
- Include a convalescent visit for participants with confirmed SARS-CoV-2 infection.
- Explore the mRNA-1273 vaccine efficacy in preventing asymptomatic SARS-CoV-2 infection.
- Update the Month 7 and Month 13 visits to Day 209 and Day 394, respectively, to extend the follow-up to a full 12-month period after the second injection on Day 29 (Month 1).
- Decrease the highest dose of mRNA-1273 in the study from 250 µg to 100 µg.

The summary of changes table describes the major changes made in Amendment 1, including the sections modified and the corresponding rationale. Minor editorial or formatting changes are not included in this summary table.

Summary of Major Changes in Protocol Amendment 1:

Section # and Name	Description of Change	Brief Rationale
Title page, Signature page, and header	Updated protocol version and date.	Revised version and date of protocol.
Title page, Signature page, and header	Updated the protocol title.	Revised to reflect the current purpose of the study.
Synopsis and Section 2.3 Exploratory Objectives		Request from the Health Authority.

Section # and Name	Description of Change	Brief Rationale
Synopsis, Section 2.3 Exploratory Objectives, Section 4.3.3 Exploratory Endpoints, Section 4.6.4 Exploratory Analyses		Editorial change.
Synopsis, Section 3.1 Study Design, Study Flow Schema (Figure 1), Sentinel and Expansion Cohort Schema (Figure 2), Section 3.1.1 Rationale for Dose Selection, 3.4.1 Method of Assigning Participants to Dosing Groups. Dose Group Assignment (Table 1), 3.4.2 Investigational Product Administration, 4.5 Sample Size Determination	Decreased the highest dose of mRNA-1273 in the study from 250 µg to 100 µg.	Decreased based on the preliminary findings of the Phase 1 DMID study.
Synopsis and Section 3.1 Study Design	Deleted collection of nasopharyngeal swab samples at the Screening Visit (Day 0).	Editorial update for consistency with Schedule of Events (Table 7).
Synopsis and Section 3.1 Study Design	Deleted the number of visits at which participants will have blood samples collected.	Editorial update to avoid confusion as blood samples will be collected at different visits for safety and vaccine immunogenicity assessments.
Synopsis; Section 3.1 Study Design, Section 3.5.6 Blood Sampling Volumes (Table 3), Section 3.5.7 Safety Assessments, Section 3.5.8.6 Eliciting and Documenting Adverse Events, Section 4.3.1.2 Primary Immunogenicity Endpoint, Section 4.3.2 Secondary Endpoints, Section 4.7 Interim Analyses, Section 6.4 Clinical Study Reports, and Section 7.1 Appendix 1: Schedule of Events (Table 7)	Updated Month 7 and Month 13 visits to Day 209 and Day 394, respectively, to allow for 6-month and 12-month intervals, respectively, after the second injection on Day 29 (Month 1).	Request from the Health Authority.
Synopsis, Section 3.1 Study Design, and Section 7.1 Appendix 1: Schedule of Events (Table 7)	Updated the biweekly safety telephone calls from Day 211 through Day 351 to Day 223 through Day 377.	Consequent to the change made to the Day 209 Visit (Request from the Health Authority).

Section # and Name	Description of Change	Brief Rationale
Synopsis, Section 3.1 Study Design, Section 3.1.2 Rationale for Study Design, Section 3.5.1 Assessment for SARS-CoV-2 Infection, and Section 7.1 Appendix 1: Schedule of Events (Table 7)	Updated nasal swab to nasopharyngeal swab.	Clarified the type of swab to be performed.
Section 3.1.1 Rationale for Dose Selection	Updated enrollment and preliminary safety data from the ongoing Phase 1 DMID study.	Updated based on the preliminary findings of the Phase 1 DMID study.
Section 3.2.1 Inclusion Criteria	Updated inclusion criterion #7 to exclude sperm donations through 3 months after the last injection.	Update to align with the informed consent form on refraining male participants from sperm donation through 3 months after the last injection based on IRB feedback to the ICF.
Section 3.3.2 Handling Withdrawal From the Study	Updated the scheduled end of study assessments at Day 394 (Month 13) to allow for a 12-month interval after the second vaccination on Day 29 (Month 1).	Request from the Health Authority.
Section 3.4.5 Blinding	Updated the method to maintain the blind of the dosing assignment from opaque sleeve to blinding label.	Operational change in cases for which opaque sleeves are not used.
Section 3.5.1 Assessment for SARS-CoV-2 Infection	
 Added more intense monitoring of participants who are confirmed to have SARS-CoV-2 infection (ie, notification of the participant's primary care physician by the investigator and recording of confirmed SARS-CoV-2 infection as an MAAE along with relevant concomitant medications and details about severity, seriousness, and outcome). Added a convalescent visit with blood collection after diagnosis of SARS-CoV-2 infection. 	Request from the Health Authority.
Section 3.5.1 Assessment for SARS-CoV-2 Infection and Section 3.5.8.2 Medically Attended Adverse Event	Deleted "or COVID-19."	Editorial update for internal consistency.
Section 4.3.3 Exploratory Endpoints		Request from the Health Authority.

Section # and Name	Description of Change	Brief Rationale
Section 7.1 Appendix 1: Schedule of Events (Table 7)	Deleted that Day 0 and Day 1 visits may be combined the same day.	Editorial update of template text, which did not apply to this protocol.
	Corrected sequential footnote numbering in the schedule of events (Table 7).	Editorial update.
	Included a header row titled “Days Since Most Recent Vaccination.”	Update to clarify that the visits are relative to the most recent injection.

Abbreviation: DMID = Division of Microbiology and Infectious Diseases; ICF = informed consent form; IRB = Institutional Review Board; MAAE = medically attended adverse event; SARS-CoV-2 = Severe Acute Respiratory Syndrome coronavirus that causes COVID-19.

TEAE	treatment-emergent adverse event
ULOQ	upper limit of quantification
WHO	World Health Organization
WHODD	World Health Organization drug dictionary

1. Introduction

This statistical analysis plan (SAP), which describes the planned analyses for Study mRNA-1273-P201, is based on the most recent approved clinical study protocol (CSP), Version Amendment 6, dated 28-APR-2021. The most recent approved electronic case report form (eCRF) Version 5.005, dated 24-FEB-2021. It is noted that the scope of this SAP is covering Part A and Part B. The SAP for Part C is provided in a separate document.

The main purpose of this SAP amendment (Version 5.0) is to add: 1) seroresponse definition based on pre-Dose 1 of primary series for Part B booster subjects; and 2): within subject comparison on immunogenicity data for Part B booster subjects. There is no change for Part A since Part A has been completed and a CSR (Day 57) and End of Part A CSR addendum (Addendum 1, 13 Aug 2021) have been finalized.

[Table 1](#) provides a summary of major changes.

Table 1: Summary of major changes in SAP Version 5.0 (for Part B only)

Section	Brief Description of Changes
6.4	Add seroresponse definition based on pre-dose Day 1 of primary series for booster subjects Clarify that analysis for seroresponse rate for Part B booster subjects will be based on 3 definitions of seroresponse
6.4.2	For Part B booster subjects, add within subject comparison on immunogenicity data between Day 29 after booster dose and their own immunogenicity data on Day 57 of primary series

In addition to the information presented in the statistical analysis plan section of the protocol (Section 4) which provides the principal features of analyses for this study, this SAP provides statistical analysis details/data derivations. It also documents modifications or additions to the analysis plan that are not “principal” in nature and result from information that was not available at the time of protocol finalization.

Study mRNA-1273-P201 is a Phase 2a, randomized, observer-blind, placebo-controlled, dose-confirmation study to evaluate the safety, reactogenicity, and immunogenicity of messenger ribonucleic acid (mRNA)-1273 SARS-CoV-2 vaccine in adults who aged 18 years and older.

PPD Biostatistics and programming team, designee of Moderna Biostatistics and Programming department, will perform the statistical analysis of the safety, reactogenicity, and immunogenicity data; Statistical Analysis System (SAS) Version 9.4 or higher will be used to generate all statistical outputs (tables, figures, listings, and datasets). The SAP will be finalized and approved prior to the primary analysis clinical database lock and treatment unblinding for the study. If the methods in this SAP differ from the methods described in the protocol, the SAP will prevail.

2. Study Objectives

2.1. Primary Objective (Part A, Blinded)

2.1.1. Primary Safety Objective

The primary safety objective is to evaluate the safety and reactogenicity of 2 dose levels of mRNA-1273 vaccine, each administered in 2 doses 28 days apart.

2.1.2. Primary Immunogenicity Objective

[figure not shown]
The primary immunogenicity objective is to evaluate the immunogenicity of 2 dose levels of mRNA-1273 vaccine, each administered in 2 doses 28 days apart, as assessed by the level of specific binding antibody (bAb).

2.2. Secondary Objectives (Part A, Blinded)

The secondary immunogenicity objective is to evaluate the immunogenicity of 2 dose levels of mRNA-1273 vaccine, each administered in 2 doses 28 days apart, as assessed by the titer of neutralizing antibody (nAb).

2.3. Exploratory Objectives (Part A, Blinded)

The exploratory objectives are the following:

2.4. Primary Objective (Part B, Open Label)

2.4.1. Primary Safety Objective

The primary safety objective is to evaluate the safety and reactogenicity of 50 µg of mRNA-1273 vaccine administered as a single booster dose or 100 µg of mRNA-1273 vaccine administered as 2 doses 28 days apart.

2.4.2. Primary Immunogenicity Objective

[figure not shown]
The primary immunogenicity objective is to evaluate the immunogenicity of 50 µg of mRNA-1273 vaccine administered as a single booster dose or 100 µg of mRNA-1273 vaccine administered as 2 doses 28 days apart, as assessed by the level of specific bAb.

2.5. Secondary Objectives (Part B, Open Label)

The secondary objective is to evaluate the immunogenicity of 50 µg of mRNA-1273 vaccine administered as a single booster dose or 100 µg of mRNA-1273 vaccine administered as 2 doses 28 days apart, as assessed by the titer of nAb.

2.6. Exploratory Objectives (Part B, Open Label)

The exploratory objectives are the following:

3. Study Endpoints

3.1. Primary Endpoints (Part A, Blinded)

3.1.1. Primary Safety Endpoints

The primary safety objective will be evaluated by the following safety endpoints:

- Solicited local and systemic adverse reactions (ARs) through 7 days after each injection.
- Unsolicited adverse events (AEs) through 28 days after each injection.
- Medically-attended AEs (MAAEs) through the entire study period.
- Serious AEs (SAEs) throughout the entire study period.
- Safety laboratory abnormalities at Day 29 and Day 57 (Cohort 2 only).
- Vital sign measurements and physical examination findings.

3.1.2. Primary Immunogenicity Endpoints

Level of SARS-CoV-2-specific bAb measured by enzyme-linked immunosorbent assay (ELISA) on Day 1, Day 29 (M1), Day 43, Day 57 (M2), Day 209 (M7), and Day 394 (M13), as applicable.

[figure not shown]
3.2. Secondary Endpoints (Part A, Blinded)

The secondary objective will be evaluated by the following endpoints:

- Titer of SARS-CoV-2-specific nAb on Day 1, Day 29 (M1), Day 43, Day 57 (M2), Day 209 (M7), and Day 394 (M13), as applicable.
- Seroconversion on Day 29 (M1), Day 43, Day 57 (M2), Day 209 (M7), and Day 394 (M13) as measured by an increase of SARS-CoV-2-specific nAb titer either from below the lower limit of quantification (LLOQ) to equal to or above LLOQ, or a 4-times higher titer in participants with pre-existing nAb titers, as applicable.

3.3. Exploratory Endpoints (Part A, Blinded)

The exploratory endpoints are the following:

3.4. Primary Endpoints (Part B, Open Label)

3.4.1. Primary Safety Endpoints

The primary safety objective will be evaluated by the following safety endpoints:

- Solicited local and systemic ARs through 7 days after each injection.
- Unsolicited AEs through 28 days after each injection.
- MAAEs through the entire study period.
- SAEs throughout the entire study period.
- Vital sign measurements and physical examination findings.

3.4.2. Primary Immunogenicity Endpoints

- For participants receiving 100 µg of mRNA-1273 as 2 doses 28 days apart: Level of SARS-CoV-2-specific bAb measured by ELISA on OL-Day 1, OL-Day 8, OL-Day 15, OL-Day 29 (OL-M1), OL-Day 57 (OL-M2), and OL-Day 209 (OL-M7).
- For participants receiving 50 µg of mRNA-1273 as a single booster: Level of SARS-CoV-2-specific bAb measured by ELISA on OL-Day 1, OL-Day 8, OL-Day 15, OL-Day 29 (OL-M1), OL-Day 57 (OL-M2), and OL-Day 181 (OL-M6).

3.5. Secondary Endpoints (Part B, Open Label)

The secondary objective will be evaluated by the following endpoints:

- For participants receiving 100 µg of mRNA-1273 as 2 doses 28 days apart: Titer of SARS-CoV-2-specific nAb on Open Label (OL)- Day 1, OL-Day 8, OL- Day 15, OL- Day 29 (OL-M1), OL- Day 57 (OL-M2), and OL- Day 209 (OL-M7).
- For participants receiving 50 µg of mRNA-1273 as a single booster: Titer of SARS-CoV-2-specific nAb on OL-Day 1, OL-Day 8, OL-Day 15, OL-Day 29 (OL-M1), OL-Day 57 (OL-M2), and OL-Day 181 (OL-M6).
- For participants receiving 100 µg of mRNA-1273 as 2 doses 28 days apart: Seroconversion on OL-Day 8, OL-Day 15, OL-Day 29 (OL-M1), OL-Day 57 (OL-M2), and OL-Day 209 (OL-M7).
- For participants receiving 50 µg of mRNA-1273 as a single booster: Seroconversion on OL-Day 8, OL-Day 15, OL-Day 29 (OL-M1), OL-Day 57 (OL-M2), and OL-Day 181 (OL-M6), and the proportion of participants with a ≥ 2 -, ≥ 3 -, or ≥ 4 -fold rise in antibody titer from open-label baseline.

3.6. Exploratory Endpoints (Part B, Open Label)

The exploratory endpoints are the following:

A large rectangular area of the page is completely blacked out, indicating that the content has been redacted for privacy or legal reasons.

4. Study Design

4.1. Overall Study Design

This is a three-part, Phase 2a study: Part A, Part B, and Part C. Participants in Part A, the Blinded Phase of the study, are blinded to their treatment assignment. Given that the primary efficacy endpoint for mRNA-1273 against COVID-19 was met in a separate Phase 3 efficacy study (COVE study) conducted by the Sponsor, this Phase 2a study will move to Part B, Open-Label Interventional Phase.

Part B, the Open-label Interventional Phase of this study is designed to offer participants who received placebo in Part A of this study an option to receive 2 injections of open-label mRNA-1273. Participants who received 1 or 2 injections of mRNA-1273 (50 µg or 100 µg) in Part A of this study will proceed to Part B, open-label, and will be offered a single booster dose of mRNA-1273 (50 µg).

Part C, the Open-Label Interventional Phase of the study of mRNA-1273.351 and mRNA-1273/mRNA-1273.351 mixture booster vaccines is a Proof-of-Concept rollover study of approximately 60 participants, who enrolled in Moderna's Phase 3 mRNA-1273-P301 COVE study, and have previously received 2 doses of mRNA-1273 at least 6 months earlier.

4.1.1. Part A, the Blinded Phase

Part A, the Blinded Phase of this study is an observer-blind, randomized, and placebo-controlled, with adult participants at least 18 years of age. The study schematic is presented in [Figure 1](#).

Two dose levels (50 µg and 100 µg), will be evaluated in this study, based in part on initial safety data from the Phase 1 study of mRNA-1273. The study will include 2 age cohorts: Cohort 1 with 300 participants (≥ 18 to < 55 years old) and Cohort 2 with 300 participants (≥ 55 years old). Approximately 600 participants will receive either mRNA-1273 vaccine or saline placebo control according to a 1:1:1 randomization ratio; ie, within each age cohort, 100 participants will receive mRNA-1273 50 µg, 100 participants will receive mRNA-1273 100 µg, and 100 participants will receive saline placebo.

The study will be initiated with a parallel enrollment of all 300 participants in Cohort 1 (≥ 18 to < 55 years old) and a sentinel group of 50 participants in Cohort 2 (≥ 55 years old) receiving study treatment ([Figure 2](#)). Before initiating study treatment of the remaining participants in Cohort 2, safety data through Day 7 from the sentinel group of Cohort 2 and all available data from Cohort 1 will be reviewed by the Safety Monitoring Committee (SMC).

If no safety concerns are found, expansion enrollment (N=250) of Cohort 2 will proceed.

Figure 1 Study Design Schematic

[figure not shown]
[figure not shown]

Figure 2: Sentinel and Expansion Cohort Schema

4.1.2. Part B, the Open-Label Interventional Phase

[figure not shown]
Part B, the Open-Label Interventional Phase of the study, is prompted by the authorization of a COVID-19 vaccine under an EUA. Transitioning the study to Part B permits all ongoing study participants to be informed of the availability and eligibility criteria of any COVID-19 vaccine made available under an EUA and the option to offer all ongoing study participants an opportunity to schedule a Participant Decision Visit to know their original treatment assignment (placebo vs. mRNA-1273 [50 µg or 100 µg] vaccine).

Part B, the Open-Label Interventional Phase of the study, provides the opportunity for study participants who previously received placebo to actively request to receive 2 doses of mRNA-1273 (100 µg) vaccine. In addition, all participants who previously received 1 or 2 injections of mRNA-1273 (50 µg or 100 µg) vaccine will be able to receive a single booster dose of mRNA-1273 (50 µg). All study participants will receive a Notification

Letter summarizing the basis for a COVID-19 vaccine to receive an EUA and will be asked to schedule a Participant Decision Clinic Visit.

After the Participant Decision Clinic Visit (Protocol Table 10), all participants will proceed to the open-label Part B of the study and will follow the Part B Schedule of Events (Protocol Table 11 or Table 12) as follows ([Figure 3](#)).

Figure 3: Part B, Open-Label Schema

4.1.3. Part C, the Open-Label Interventional Phase

Part C, the Open-Label Interventional Phase of the study of mRNA-1273.351 and mRNA-1273/mRNA-1273.351 mixture booster vaccines, is prompted by the need to pro-actively prepare for vaccination strategies that induce a broader protection, including variants such as B.1.351. Upon consent to roll over, Participants in Part C will receive a single booster dose of either mRNA-1273.351 (20 µg or 50 µg), or mRNA-1273/mRNA-1273.351 mixture (50 µg total). An additional booster dose may be added approximately 56 days after the first boost at OL-Day 1. This additional booster dose will be triggered following review of immunogenicity data up to OL-Day 15 of the initial mRNA-1273.351 (20 µg and 50 µg) and mRNA-1273/mRNA-1273.351 mixture injections. The enrollment and vaccination in each study arm will be sequential. The first 20 participants will be enrolled and dosed on OL-Day 1 with mRNA-1273.351 50 µg dose. Upon completion of the first 50 µg dose arm, 20 participants will be enrolled in the second arm and will receive the mRNA-1273/mRNA-1273.351 mixture (50 µg total dose). Following completion of the

second arm, 20 participants will be enrolled and dosed with in the mRNA-1273.351 20 μ g dose.

4.2. Sample Size and Power

There is no hypothesis testing in this study. The number of proposed participants is considered sufficient to provide a descriptive summary of the safety and immunogenicity of different dose levels of mRNA-1273.

In Part A, approximately 600 participants will be randomly assigned in a 1:1:1 ratio to mRNA-1273 50 μ g, mRNA-1273 100 μ g, or placebo. A total of 400 participants will receive mRNA-1273, 200 participants in each dose level, or 100 participants in each age cohort and dose level. [Table 2](#) presents the 95% confidence interval (CI) for 1 participant with an AE and the lowest AE rate detectable with at least 95% probability for each selected sample size. The 2-sided 95% CI was calculated using the Clopper-Pearson method for one proportion in SAS 9.4 software. The 2-sided 95% CI is estimated (0.01%, 1.38%) at sample size of 400 with 1 participant reporting an AE. Furthermore, a sample size of 400 has at least a 95% probability to observe at least 1 participant with an AE at a true 0.75% AE rate.

Table 2: 95% Confidence Interval for One Participant with AE and the Lowest Detectable Incidence Rate at 95% Probability in Selected Sample Size

Sample Size Receiving mRNA-1273	Rate and 95% CI (%) at One Participant with AE			Lowest Detectable Rate (%) with \geq 95% Probability
	AE Rate	Lower CI	Upper CI	
100	1.00	0.03	5.45	2.95
200	0.50	0.01	2.75	1.49
400	0.25	0.01	1.38	0.75

In the open-label Part C, approximately 60 participants from Moderna's mRNA-1273-P301 COVE study, will be enrolled and will be assigned to receive a single intramuscular injection of mRNA-1273.351 (20 μ g or 50 μ g) or mRNA-1273/mRNA-1273.351 mixture (50 μ g total). The enrollment and vaccination in each study arm will be sequential. The first 20 participants will be enrolled and dosed on OL-Day 1 with mRNA-1273.351 50 μ g dose. Upon completion of the first 50 μ g dose arm, 20 participants will be enrolled in the

second arm and will receive the mRNA-1273/mRNA-1273.351 mixture (50 µg total dose). Following completion of the second arm, 20 participants will be enrolled and dosed with the mRNA-1273.351 20 µg dose.

4.3. Randomization

There are two age cohorts in this study: participants ≥ 18 to < 55 years old in Cohort 1 and participants ≥ 55 years old in Cohort 2. Within each age cohort, approximately 300 participants will be randomized in 1:1:1 ratio to receive mRNA-1273 50 µg, mRNA-1273 100 µg, or placebo. The randomization will be in a blinded manner using a centralized Interactive Response Technology (IRT), in accordance with pre-generated randomization schedules.

4.4. Blinding and Unblinding

Part A of this study is observer-blind. The investigator, study staff, study participants, site monitors, and Sponsor personnel (or its designees) will be blinded to the investigational product administered until study end or initiation of Part B, with certain exceptions, please refer to Section 3.4.5 of the protocol for details. There is a planned primary analysis when all subjects completed Day 57 Visit in Part A and a final analysis at end of study. At time of primary analysis, only pre-identified Sponsor and unblinded Contract Research Organization (CRO) team members as specified in the study Data Blinding Plan will be unblinded to review treatment level results and individual listings, please also refer to Section 6.6. Study sites will remain blinded to individual treatment assignments until the end of the study or the initiation of Part B.

5. Analysis Populations

The following analysis sets are defined: Randomized Set, Solicited Safety Set, Safety set, Full Analysis set (FAS), and Per-Protocol (PP) set.

5.1. Randomized Set

The Randomized Set consists of all participants who are randomized in the study, regardless of the participant's treatment status in the study. Subjects will be included in the vaccination group to which they were randomized.

5.2. Solicited Safety Set

Solicited Safety Set (Part A, Blinded Phase)

The Solicited Safety Set for Part A consists of all participants who are randomized and received any study injection during Part A, and contribute any solicited AR data, ie, have at least one post-baseline solicited safety assessment in Part A. The Solicited Safety Set will be used for the analyses of solicited ARs and subjects will be included in the vaccination group corresponding to the study injection they actually received during Part A. In addition, the following Solicited Safety Set is defined for each injection separately.

The First (Second) Injection Solicited Safety Set for Part A consists of all subjects in the Solicited Safety Set (Part A) who have received the first (second) study injection during Part A and have contributed any solicited AR data from the time of first (second) study injection through the following 6 days.

Subjects will be analyzed according to the vaccination group a subject received during Part A, rather than the vaccination group to which the subject was randomized. Subjects who receive a second injection that is different from the first injection will be summarized under the higher dose of vaccination group (eg, Placebo < mRNA-1273 50 µg < mRNA-1273 100 µg).

Solicited Safety Set (Part B, Open-Label Phase)

The Solicited Safety Set for Part B consists of all participants who are randomized in Part A and received any study injection during Part B, and contribute any solicited AR data, ie, have at least one post-baseline solicited safety assessment in Part B. The Solicited Safety Set will be used for the analyses of solicited ARs and subjects will be included in the vaccination group corresponding to the study injection they actually received in Part B, 100 µg of mRNA-1273 as 2 doses injection (for participants who received placebo injection in Part A) vs booster dose.

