4.4.2 Solicited Safety Set

The Solicited Safety Set consists of all participants who are randomly assigned and received any study injection, and contribute any solicited AR data; ie, have at least one post-baseline solicited safety (eDiary) assessment. The Solicited Safety Set will be used for the analyses of solicited ARs and participants will be included in the treatment group corresponding to the study injection they actually received. This analysis set will be used for analyses in Part A, Part B and Part C.

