If a subject received any study vaccination injection that is at a non-protocol dose in Part A, the subject will be assigned to a protocol dose (Placebo, mRNA-1273 vaccine 50 µg, or mRNA-1273 vaccine 100 µg) for that injection according to the following rule:

- mRNA-1273 50 µg if the received dose > 0 µg and <= 75 µg, or
- mRNA-1273 100 µg if the received dose > 75 µg

Summary by age cohort:

All analyses and data summaries/displays will be provided by vaccination group for overall (the 2 age cohorts combined) and for each age cohort (>= 18 to < 55 years old, >= 55 years old), unless otherwise specified.

All analyses will be conducted using SAS Version 9.4 or higher.

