All solicited ARs analyses will be based on the Solicited Safety Set. All solicited ARs analyses will be provided by age cohort and vaccination group as defined in [Section 6.1](#) for each injection (first or second) (Part A only) and any injection (Part A and Part B separately), unless otherwise specified.

The number and percentage of subjects who reported each individual solicited local AR (has a severity grade of Grade 1 or greater) and solicited systemic AR (has a severity grade of Grade 1 or greater) during the 7-day follow-up period after each injection will be tabulated by age cohort, vaccination group, severity grade, and injection. The number and percentage of subjects who reported each individual solicited AR will also be summarized by age cohort, vaccination group, severity grade, day of reporting and injection. The number and percentage of subjects experiencing fever (a temperature greater than or equal to 38.0°C/100.4°F by the oral, axillary, or tympanic route) by severity grade will be provided.

A two-sided 95% exact confidence interval (CI) using the Clopper-Pearson method will be provided for the percentage of subjects who reported any solicited local AR, solicited systemic AR, or any solicited AR.

The onset of individual solicited AR is defined as the time point after each injection at which the respective solicited AR first occurred. The number and percentage of subjects with onset of individual solicited AR will be summary by age cohort, vaccination group, study day relative to the corresponding injection (Day 1 through Day 7), and injection.

The number of days reporting each solicited AR will be summarized descriptively and for the following time windows (1-2 days, 3-4 days, 5-6 days, and ≥ 7 days) by age cohort, vaccination group, and injection. The number of days will be calculated as the days of the solicited AR is reported within the 7 days of injection including the day of injection, no matter it is intermittent or continued. If the solicited AR continues beyond 7 days, the consecutive days a solicited AR is reported after 7 days will be included (eg, an event that lasted 5 days in the first 7 days post injection and 3 consecutive days beyond 7 days post injection, the duration will be reported as 8 (5+3) days.)

The number and percentage of subjects who reported solicited rash and lymphadenopathy assessed by healthcare provider will be summarized by age cohort, vaccination group, severity grade, and injection.

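### The SAP's higher-dose rule for mixed Part A injections also governs the first-injection reactogenicity tables, where it files reactions to placebo or 50 µg under a higher dose given only later

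*SAP*

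**What the plan says.** SAP (Parts A and B) Section 5.2 builds the Part A Solicited Safety Set and then goes further: "In addition, the following Solicited Safety Set is defined for each injection separately". Membership of the First (Second) Injection set requires that participants "have contributed any solicited AR data from the time of first (second) study injection through the following 6 days". Neither set has a grouping rule of its own.

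The paragraph that follows supplies the only rule available to them. It works at participant level, by what each person received over the whole of Part A and not by the arm assigned, and it settles mixed cases thus: "Subjects who receive a second injection that is different from the first injection will be summarized under the higher dose of vaccination group". The order given is placebo, then 50 µg, then 100 µg.

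Section 6.3.2.1 uses these sets for tables by first, second and any injection in Part A. Individual local and systemic reactions "will be tabulated by age cohort, vaccination group, severity grade, and injection".

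Section 6.1 has a separate rule for doses that match no protocol dose. It assigns a protocol dose "for that injection according to the following rule": up to 75 µg counts as 50 µg, and above 75 µg counts as 100 µg.

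Protocol Section 4.4.2 says only that "participants will be included in the treatment group corresponding to the study injection they actually received". It has no higher-dose rule, and SAP Section 7 does not list that rule among the changes from the protocol.

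**The concern.** A single label per person is reasonable when the table covers any injection or the whole of Part A. It does not suit a table confined to the first injection. At that point the participant has received one product, and the label can be set by a different product given about four weeks later.

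Solicited reactions after each injection are a primary safety endpoint of a dose-confirmation study. The per-injection tables are there to show how reactions vary with dose and injection number. Protocol Section 1.3 describes Phase 1 reactions as generally dose dependent and generally increasing after the second injection. If that holds here, the rule is not conservative for the first injection. It pulls the higher-dose column down with reactions to a milder product, and it removes a valid record from the column where that record belongs.

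**Working it through.** **Published figure.** The plan states no figure that depends on this rule. Its only sample-size figures are in SAP Table 2, and they reproduce. The Clopper-Pearson limits for one event are 0.025% to 5.446% at n = 100, 0.013% to 2.754% at n = 200 and 0.006% to 1.385% at n = 400. The lowest detectable rates, 1 − 0.05^(1/n), are 2.951%, 1.487% and 0.746%. The point does not rest on them.

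**Where the rule puts each first-injection record**

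| Day 1 → Day 29 | Given at first injection | First-injection column under Section 5.2 |
|---|---|---|
| Placebo → 50 µg | Placebo | 50 µg |
| Placebo → 100 µg | Placebo | 100 µg |
| 50 µg → 100 µg | 50 µg | 100 µg |
| 50 µg → off-protocol dose above 75 µg | 50 µg | 100 µg (Section 6.1 codes the second injection as 100 µg; Section 5.2 then relabels the person) |
| Higher → lower product | Higher product | Higher product (correct) |

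Section 6.1 does not rescue the first four rows, since it only maps an off-protocol dose to a protocol dose. It does show that coding by injection already exists in the plan.

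**Size.** Suppose m of the N people in a column received another product at that injection. The expected shift is

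(m/N) × (rate after the product given − rate after the column's product).

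SAP Section 4.2 gives N = 100 per age cohort and dose level, and N = 200 per dose level. The documents give neither m nor the rates, so those are assumptions. The bound for one person is 1/N: 1/100 = 1.0 point and 1/200 = 0.5 point.

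Expected fall in the 100 µg first-injection rate, in percentage points:

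| Assumed rates (100 µg, placebo) | N=100, m=1 | N=100, m=5 | N=200, m=1 | N=200, m=5 |
|---|---|---|---|---|
| 90%, 40% | 0.5 | 2.5 | 0.25 | 1.25 |
| 80%, 20% | 0.6 | 3.0 | 0.3 | 1.5 |
| 50%, 10% | 0.4 | 2.0 | 0.2 | 1.0 |
| 100%, 0% (limit) | 1.0 | 5.0 | 0.5 | 2.5 |

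A further example assumes 85% and 20% with N = 100. One case gives (0.85 × 99 + 0.20 × 1)/100 = 84.35%. Five cases give (0.85 × 95 + 0.20 × 5)/100 = 81.75%. For comparison, the Clopper-Pearson 95% interval for 85 of 100 is 76.5% to 91.4%, about 15 points wide.

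**The case against.** **Cross-dosing may never have happened.** Allocation was central, dedicated unblinded pharmacy staff prepared and gave the injections, and receipt of the full dose was confirmed (Protocol Sections 3.3.1, 3.3.5 and 3.3.7). Protocol Section 1.3 reports 200 first injections per group and 195, 198 and 194 second injections, with no mention of mixed products. This stands: it does not prove there were none, but nothing shows there were any.

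**The effect is small and nothing is tested.** This also stands. One or two cases would be lost within the width of the interval.

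**A reader might infer that the SAP contradicts the protocol.** The documents do not support that. Protocol Section 4.4.2 speaks of one injection and does not say what to do when two differ. The higher-dose rule fills the gap with a product the person did receive. The protocol leaves detail to the SAP, and SAP Section 1 gives the SAP precedence where methods differ. What remains is a misfit with the principle of grouping by what was received.

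**A reader might also infer that every per-injection table should simply be regrouped by product.** For second injections that is a trade-off. Someone given placebo and then 100 µg is having a first vaccine exposure at Day 29. Someone given 100 µg and then placebo is not comparable with a placebo recipient who was never vaccinated. Neither grouping is clean.

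**Mixed cases can be found in the listings.** Vaccine administration, major deviations and solicited reactions are all listed (SAP Sections 6.2.5, 6.2.6 and 6.3.2.1). That helps a reader trace such a person but does not correct the table.

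None of these answers the first-injection case, where a later product decides the column for earlier reactions.

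**Conclusion.** The point holds for the first-injection tables. Section 5.2 does not say in so many words that the higher-dose rule reaches the per-injection sets. That reading follows because the rule comes directly after those sets are defined, is the only grouping rule they could use, and carries no exception. The same rule in the Safety Set (SAP Section 5.3) does no such harm, since no per-injection set is defined there.

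The importance is modest and conditional. Dilution of the higher-dose column assumes that the higher dose is the more reactogenic. The effect is zero if nobody received two different products. It would be wrong to conclude that the reported Part A reactogenicity is biased: the documents give no count of such participants.

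**What to change.** SAP Section 1 states that Part A is complete and that the Day 57 report and the End of Part A addendum are final, so the order of work matters.

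1. Count the Part A participants whose two injections differed, using the recorded dosing data. If there are none, say so in a footnote; no table changes.
2. Amend SAP Section 5.2 so that first-injection summaries classify participants by the product and dose received at the first injection, coded as in Section 6.1, and the higher-dose rule is limited to any-injection and overall summaries.
3. For second-injection summaries, either footnote each mixed-product participant with the injection sequence, or add a sensitivity table by product received at that injection.
4. If there are any such participants, re-tabulate the Part A first-injection solicited reaction tables in the end-of-study report, labelled as a post hoc correction. Protocol Section 6.4 has that report cover Part A from Day 0 to Day 394.

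The cost is a short SAP amendment and a count, with a limited re-run only if the count is not zero. No new data are needed. The drawback is that a participant may sit in different columns in the first-injection and any-injection tables, which a footnote should explain.
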